2.3. Study Design

This is an open label, dose-seeking phase 1/2 study using a defined dose of nivolumab and escalating doses of ABI-009 given intravenously.

I. Dose Escalation Phase 1 Part of Study: The study will employ the standard "cohort of three" design (Storer, 1989). Three patients are treated at each dose level with expansion to six patients per cohort if DLT is observed in one of the three initially-enrolled patients at each dose level. If no DLT occurs after 2 doses, escalation to the next dose level will be permitted. The maximum tolerated dose is defined as the highest safely tolerated dose, where not more than one patient experienced DLT, with the next higher dose level having at least two patients who experienced DLT. Patients in the dose escalation study may continue treatment at their designated dose levels up to eighteen 3-week treatment cycles or until significant disease progression or unacceptable toxicity occurs. No intra-patient dose escalation will take place.

Dose of nivolumab: 3 mg/kg IV over 30 min. q 3 weeks

NB: ABI-009 will start after 2nd Nivo dose, and will be administered on D8 and D15 beginning in C2.

Dose of ABI-009: Escalating doses IV over 30 min for 2 of every 3 weeks:

Treatment Cycle	# Pts.	Dose Level	Dose, mg/m2
Every 3 weeks	3-6	I	56
Every 3 weeks	3-6	II	75
Every 3 weeks	3-6	III	100

Note: DLT includes any \geq Grade 3 colitis, hepatitis, or pneumonitis, any Grade 1-2 colitis, hepatitis or pneumonitis that recurs, worsens or persists with oral steroids longer than 14 days, symptoms of adrenal crisis, any Grade 4 hematologic toxicity or any \geq Grade 3 non-hematologic toxicity.

II. Expansion Phase 2 Part of Study: Following dose escalation, an additional 22-28 patients will receive ABI-009 at the MTD and defined doses of nivolumab to assess overall safety and potential efficacy in a greater number of patients. Patients in the expansion

phase of the study may continue treatment up to 18 3-week treatment cycles or until significant disease progression or unacceptable toxicity occurs.

The study will be conducted in compliance with International Conference on Harmonisation (ICH) Good Clinical Practices (GCPs).

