2.5. End of Study, End of Treatment, End of Treatment Visit, Follow-up Period

End of Study (EOS) is defined as either the date of the last visit of the last patient to complete the study, or the date of receipt of the last data point from the last patient that is required for primary, secondary, and/or exploratory analysis, as pre-specified in the protocol.

End of Treatment (EOT) is defined as the date of the last dose of ABI-009 or nivolumab for an individual patient

End of Treatment Visit for a patient is when safety assessments and procedures are performed after the last treatment, which must occur at least 4 weeks (\pm 7 days) after the last dose of ABI-009 or nivolumab.

Primary analysis for this study will occur after all patients have either completed the study or completed 12 months of treatment. Patients who are still active at the time of the primary analysis may continue on study until disease progression or medication intolerance is observed.

Primary Completion is the time when the last patient is assessed or receives an intervention for the purposes of final collection of data for the primary analysis.

Follow-up period is the on-study time period after the EOT Visit. All patients that discontinue study drug and have not withdrawn full consent to participate in the study will continue in the follow-up phase for survival and anticancer therapy. Follow-up will continue approximately every 12 weeks (+/- 3 weeks), or more frequently as needed, until death, withdrawal of consent, or the study closes, whichever is the earliest. This evaluation may be made by record review and/or telephone contact.

The final patient's last visit for the study will be defined as whichever of the following represents the last time point:

- When the last patient on study has completed their Safety follow-up visit, or
- When the last patient on study has documented toxicities to ABI-009 and nivolumab, and the toxicity has resolved, returned to baseline or is deemed irreversible after the Safety follow-up visit or
- When the last patient completes or discontinues the follow-up phase

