6. DESCRIPTION OF STUDY TREATMENTS (ABI-009/NIVO)

6.1. ABI-009/Nivolumab Dosage, Administration, and Schedule

For the Phase 1 part of study, patients will receive nivolumab 3 mg/kg as IV infusion over 60 min every 3 weeks, followed by escalating doses of ABI-009 56, 75, 100 mg/m² for 2 of every 3 weeks by IV infusion over 30 minutes. ABI-009 will start on Day 8 of Cycle 2. If DLT develops in more than 1 patient at Dose 56 mg/m², the dose will be de-escalated to 45 mg/m² and to 30 mg/m² if DLT develops at 45 mg/m². Patients will continue therapy until unequivocal clinical disease progression, unacceptable toxicity, or until in the opinion of the investigator the patient is no longer benefiting from therapy, or at the patient's discretion.

For the Phase 2 part of study, patients will receive nivolumab 3 mg/kg as IV infusion over 30 min every 3 weeks, followed by ABI-009 at the MTD dose for 2 of every 3 weeks by IV infusion over 30 minutes. ABI-009 will start on Day 8 of Cycle 2. Patients will continue therapy until unequivocal clinical disease progression, unacceptable toxicity, or until in the opinion of the investigator the patient is no longer benefiting from therapy, or at the patient's discretion.

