6.2. ABI-009 Dose Modification and Stopping Rules

6.2.1. Dosage Adjustments, Delays, Rules for Withholding or Restarting, Permanent Discontinuation

If, treatment cannot be administered on the planned visit date, ABI-009 may be administered +/- 2 days from the scheduled date. Prior to ABI-009 administration on Day 1 of each cycle, patients must meet the following hematological requirements:

- ANC $\geq 1.5 \times 10^9/L$
- Platelet count $\geq 100 \times 10^9/L$
- Hemoglobin $\geq 9 \text{ g/dL}$

The treatment will be on hold up to 14 days until the patient has fulfilled these criteria.

If a Grade 4 hematologic toxicity occurs, the dose of ABI-009 is held until toxicity resolves to Grade 1 or less. The dose of ABI-009 is then modified according to the dose modification section. If a Grade 3 non-hematologic toxicity occurs, both nivolumab and ABI-009 are withheld until toxicity resolves to Grade 1 or less. The dose of ABI-009 is then modified according to the dose modification section. Nivolumab has no dose modification.

The maximum delay between a missed scheduled dose and the next one (whichever dose was missed) should not be longer than 14 days. Approval from the Medical Monitor is required to restart study treatment after ≥ 21 days of interruption.

During the Phase 2 part of the study, doses of ABI-009 will be reduced for hematologic and other toxicities. Two levels of dose modifications are permitted according to the criteria below. If MTD is determined to be 56 mg/m², dose reductions will occur sequentially (45 mg/m² and 30 mg/m²), there should be no direct reduction by two dose

levels. If a toxicity requiring dose modification occurs following the second dose reduction of ABI-009, further treatment should be discontinued. Dose adjustments are to be made according to the system showing the greatest degree of toxicity. Toxicities will be graded using the NCI CTCAE Version 4.03.

Guidelines for dose modifications and interruptions for management of common toxicities associated with the study treatment(s) are provided in this section:

- General guidelines for clinically significant toxicities related to study treatment

And

- Specific guidelines for adverse events of special interest, which are events that have been observed with higher frequency or severity.

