8.2. Safety Analysis

Demographic and baseline information (e.g., extent of prior therapy) on study patients will be tabulated. The number of patients studied for the Phase 1 part of study could range from 12 to 18 evaluable patients, and 22-28 evaluable patients for the Phase 2 part of the study.

For the Phase 1 part of the study, the following information will be reported for adverse events observed in the study: dose level, type (organ affected or laboratory determination, such as absolute neutrophil count), severity (by NCI Common Terminology Criteria for Adverse Events (CTCAE) Version 4.03 and most extreme abnormal values for laboratory determinations) and relatedness to study treatment. For each dose the number and percentage of patients experiencing any grade 3, 4, or 5 adverse event will be reported, as well as the number and percentage of patients who experienced selected specific types of adverse events. In addition, the DLTs will be summarized by dose level and the MTD will be determined.

The following table gives the probability of dose escalation at a single dose level as a function of the true probability of DLT at that level using the cohorts of 3 design (Objective #1) (2).

Table 1. Probability of Dose Escalation

True Rate of DLT (%)	Probability of Dose Escalation
10	0.91
20	0.71
30	0.49
40	0.31
50	0.17

For the Phase 2 part of the study, the entire treated population (Full Analysis Set) will be the analysis population for all safety analyses. Adverse events will be coded using the NIH CTCAE v4.03. Summary tables will include the number and percentage of patients with AEs, serious AEs, fatal AEs and other AEs of interest. Safety will be analyzed in all patient groups together (metastatic and locally advanced). Although this study will not be large enough to allow firm conclusions about safety or efficacy, it will provide preliminary data on safety and efficacy that will be useful in planning future studies. Frequency tables, graphs, and summary statistics will be used for outcome data.

Patient incidence of all treatment-emergent AEs will be tabulated. Tables of fatal adverse events, serious adverse events, treatment-related AEs, and adverse events leading to withdrawal from investigation product will also be provided.

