8.7. Primary Analysis

The objective of the primary analysis is to address all study objectives and it will be conducted when all patients have had the opportunity to be treated for at least 6 months. All primary, secondary, and exploratory efficacy and safety analyses will be conducted at the time of the primary analysis.

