9.4.2. Reporting Procedures for Serious Adverse Events

All suspected unexpected serious adverse reactions (SUSARs) must be reported by the Investigator to their IRB in writing, and to the FDA within 7 days as required by law.

Any AE that meets any criterion for an SAE requires the completion of an SAE Report Form in addition to being recorded on the AE page/screen of the CRF. All SAEs must be reported to AADI Drug Safety within 24 hours of the investigator's knowledge of the event by facsimile, or other appropriate method, using the SAE Report Form, or approved equivalent form. This instruction pertains to initial SAE reports as well as any follow-up reports.

The investigator is required to ensure that the data on these forms is accurate and consistent. This requirement applies to all SAEs (regardless of relationship to IP) that occur during the study (from the time of signing of the informed consent form to 28 days after the last dose of IP), and those made known to the investigator at any time thereafter that are suspected of being related to IP.

The SAE report should provide a detailed description of the SAE and include a concise summary of hospital records and other relevant documents. If a patient died and an autopsy has been performed, copies of the autopsy report and death certificate are to be sent to AADI Drug Safety as soon as these become available. Any follow-up data will be detailed in a subsequent SAE Report Form, or approved equivalent form, and sent to AADI Drug Safety.

Where required by local legislation, the investigator is responsible for informing the IRB/EC of the SAE and providing them with all relevant initial and follow-up information about the event. The investigator must keep copies of all SAE information on file including correspondence with AADI and the IRB/EC.

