11.2. Institutional Review Board/Independent Ethics Committee

A copy of the protocol, proposed informed consent form, other written patient information, and any proposed advertising material must be submitted to the IRB for written approval. A copy of the written approval of the protocol and informed consent form must be received by AADI before recruitment of patients into the study and shipment of AADI IP.

The investigator must submit and, where necessary, obtain approval from the IRB for all subsequent protocol amendments and changes to the informed consent document. The investigator is to notify the IRB of deviations from the protocol or SAEs occurring at the site and other AE reports received from AADI, in accordance with local procedures.

The investigator is responsible for obtaining annual IRB approval [IRBs only]/renewal [IRBs and IECs] throughout the duration of the study. Copies of the investigator's reports and the IRB continuance of approval must be sent to AADI.

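### The Phase 2 expansion sets no number of DLTs across patients that pauses enrolment or triggers a documented review of the starting dose

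*Combined protocol and SAP*

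**What the plan says.** Section 2.3 (part II) and the matching Synopsis text state that "an additional 22-28 patients will receive ABI-009 at the MTD and defined doses of nivolumab to assess overall safety and potential efficacy". Rules that count DLTs across patients appear only for Phase 1: the cohort-of-three escalation and MTD definition in Section 2.3 (part I), and the step down from 56 to 45 and then 30 mg/m² in the Phase 1 paragraph of Section 6.1.

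For Phase 2, Section 6.2.1 says "During the Phase 2 part of the study, doses of ABI-009 will be reduced for hematologic and other toxicities". It and Sections 6.2.2 and 6.3 then set holds, reductions and discontinuation for the individual patient. Section 6.2.1 classes a Hy's Law case as a DLT but attaches no consequence for other patients.

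Oversight of the study as a whole consists of:
- continuous adverse-event reporting, including how many patients have doses changed, delayed or stopped (Synopsis, Overview of Key Safety Assessments), at one site (Section 5.1);
- medical-monitor involvement in long interruptions, continuation after unresolved toxicity, and rechallenge (Sections 6.2.1 and 6.2.2.3);
- SAE reports within 24 hours, and unexpected serious reactions that "must be reported by the Investigator to their IRB in writing, and to the FDA within 7 days as required by law" (Section 9.4.2);
- "obtaining annual IRB approval [IRBs only]/renewal [IRBs and IECs] throughout the duration of the study" (Section 11.2);
- discretionary withdrawal or termination (Sections 10.3 and 11.5).

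There are also built-in precautions: nivolumab every 3 weeks, a start two levels below the single-agent MTD (Section 1.4), and dexamethasone each cycle from Cycle 2 (Section 7.6).

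On timing, Section 8.7 states "All primary, secondary, and exploratory efficacy and safety analyses will be conducted at the time of the primary analysis". A data monitoring committee appears only in the abbreviation list.

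**The concern.** The expansion exists partly to learn about safety at the chosen dose, yet nothing obliges anyone to act on the running total. Each safeguard either treats the affected patient, transmits a single event, follows the calendar, or leaves the decision to judgement. Enrolment at one starting dose could therefore run to 22-28 patients while DLTs accumulate, with no fixed point at which the accumulation must be reviewed and the outcome recorded.

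Phase 1 gives limited assurance about that dose. It rests on very few patients, and escalation is decided after two doses. If those are ABI-009 doses, the second is planned for Cycle 2 Day 15, which is day 36. The DLTs that the protocol lists first (colitis, hepatitis, pneumonitis) tend to appear later than that.

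**Working it through.** **1. Is any Phase 2 rule based on a count?** Comparing Sections 2.3, 6.1-6.3, 8.2, 8.7, 9, 10.3 and 11 gives no number of patients with DLTs that acts on enrolment or on the starting dose in Phase 2. The closest text, the step down when more than one patient has a DLT at 56 mg/m², sits in the Phase 1 paragraph of Section 6.1. It covers that dose only and requires neither a pause nor a documented review.

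**2. Do scheduled reviews come in time?**
- Accrual: 40-50 patients (Synopsis) over about 24 months (Section 2.4) is 20-25 a year, or 1.7-2.1 a month. One IRB renewal interval spans roughly the whole of Phase 2.
- Primary analysis: Section 8.7 sets it once all patients have had the opportunity for 6 months of treatment. Section 2.5 says "Primary analysis for this study will occur after all patients have either completed the study or completed 12 months of treatment". On either wording it follows the end of enrolment.

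**3. The plan's own operating characteristic.** Section 8.2 says "The following table gives the probability of dose escalation at a single dose level as a function of the true probability of DLT". With p the true DLT rate and q = 1 - p, P(escalate) = q³ + 3pq² × q³.

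| p | Recomputed | Table 1 |
|---|---|---|
| 10% | 0.906 | 0.91 |
| 20% | 0.709 | 0.71 |
| 30% | 0.494 | 0.49 |
| 40% | 0.309 | 0.31 |
| 50% | 0.172 | 0.17 |

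Table 1 is correct.

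**4. How firm is the MTD?** The definition allows it to rest on 0/3 or 1/6. Exact (Clopper-Pearson) 95% intervals are 0-71% and 0.4-64%.

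**5. When do the named toxicities appear?** From Section 1.3.3: median pneumonitis onset 2.2 months (about day 67 at 30.4 days a month), median colitis onset 2.5 months (about day 76), hepatitis at days 86, 97 and 113. All are later than day 36.

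**6. A counting window.** Section 6.1 states "ABI-009 will start on Day 8 of Cycle 2", which is day 21 + 8 = 29. The end of Cycle 4 is day 4 × 21 = 84. The window is 56 days and holds six planned ABI-009 doses. It covers the pneumonitis and colitis medians but not the three hepatitis onsets.

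**7. Operating characteristics of the proposed bounds** (4/6, 6/12, 8/18, 10/24; the first three only when N = 22), by exact sequential binomial. Example at p = 0.40, first bound: 15(0.4)⁴(0.6)² + 6(0.4)⁵(0.6) + (0.4)⁶ = 0.138 + 0.037 + 0.004 = 0.179. The later bounds add 0.190, 0.134 and 0.096, giving 0.599 for N = 28. The first three give 0.503 for N = 22.

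| True in-window rate | Eventual pause, N = 28 | Eventual pause, N = 22 |
|---|---|---|
| 20% | 0.04 | 0.04 |
| 30% | 0.24 | 0.20 |
| 40% | 0.60 | 0.50 |
| 50% | 0.88 | 0.80 |

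Tightening the first bound to 3/6 gives 0.11, 0.35, 0.67 and 0.91 (N = 28) and 0.11, 0.32, 0.60 and 0.85 (N = 22).

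**8. Patients spared at a 40% rate.** With no rule, 0.40 × 28 = 11.2 or 0.40 × 22 = 8.8 patients with DLTs are expected. A simulation let the pause take effect as soon as a bound is met. It assumed even accrual of 1.7-2.1 patients a month and DLT onset uniform over days 29-84. It gives about 2.9-3.0 (N = 28) or 1.6-1.7 (N = 22) DLT patients avoided if enrolment does not resume at that dose. Dividing by 0.40, this is about 7 or 4 patients not enrolled. The chance that the pause comes before enrolment is full is about 0.58 or 0.48.

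**The case against.** The strongest reply is that oversight is not thin. Adverse events are followed continuously, including how many patients need dose changes. One site sees every event, the medical monitor is drawn into difficult restarts, and the investigator or sponsor can stop at any time. In a small, open-label, descriptive study, preferring a number to judgement is a design choice. All of this stands as description, and a reader who inferred that Phase 2 has no safety oversight would be wrong. What it does not supply is a stated count that makes the review automatic and documented.

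The bounds can also be criticised. They have no anchor, they allow enrolment to continue at 3/6, and at a 40% rate with 22 patients a pause is an even chance. They count only related events, although the protocol's DLT definition has no relatedness condition. The window misses the cited hepatitis onsets. These points are fair. They are reasons to treat the numbers as adjustable and to send DLTs outside the window to the review. They do not remove the gap.

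Two stronger inferences are tempting and unsupported:
- Table 1 does not give the chance that a toxic level is expanded. To become the MTD, a level must pass, the next must fail, and any lower levels must also have passed. A 40% level followed by a 50% level is selected with probability 0.309 × (1 - 0.172) = 0.256 if it is the starting dose, and less if a lower level must pass first. The true rates are unknown, so no overall expected saving can be stated.
- The 42% rate of Grade 3-4 reactions on nivolumab alone (Section 1.3.3) is not an estimate of the in-window DLT rate. It comes from dosing every 2 weeks with a median exposure of 5.3 months, and may include Grade 3 hematologic events, which are not DLTs.

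**Conclusion.** The point holds as a gap in the safety rules: Phase 2 has several safeguards, but none is a pre-specified cross-patient DLT count tied to an enrolment pause or a documented starting-dose review. Confidence in that absence is high.

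Confidence in the size of the benefit is lower. At a true in-window rate of 40%, the proposed rule spares about 3 DLT patients of 11.2 expected (N = 28) or about 1.6-1.7 of 8.8 (N = 22). This rests on even accrual, uniform onset and no resumption at that dose. If enrolment resumes after review, the saving is smaller. The documents do not give the in-window related rate. It also differs from the rate in Table 1, which drives a decision after two doses.

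A reader might infer that the missing rule undermines the planned analyses. It does not: they are descriptive, and no estimate, interval or sample size depends on it. This is a cheap improvement in patient safety that should be made.

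**What to change.** Add one paragraph to Section 2.3 (part II) and Section 8.2 to this effect:

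- **What is counted:** events meeting the DLT definition and judged related to ABI-009 or nivolumab, from the first ABI-009 dose (planned day 29) to the end of Cycle 4 (planned day 84), in order of enrolment among patients who received ABI-009.
- **When to pause:** as soon as such events have occurred in at least 4 of the first 6, 6 of the first 12, 8 of the first 18 or 10 of the first 24 patients.
- **What follows:** the investigator and the AADI medical monitor review all safety data, including related DLTs outside the window, and send the documented outcome to the IRB before enrolment resumes.

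The sponsor may tighten the bounds, for example to 3 of the first 6, and should state the toxicity rate it has in mind when doing so.

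The cost is one amendment paragraph. It uses existing staff and adverse-event data and needs no new committee. The downside is an unneeded review, with probability about 4% at a true rate of 20% and 20-24% at 30%. With 3 of 6 as the first bound these rise to about 11% and 32-35%. The rule prompts a decision about the dose; it does not make that decision.

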2.4. Study Duration

The study is expected to take approximately 32 months from first patient enrolled to last patient follow-up, including approximately 24 months of enrollment period, an estimated 6 months of treatment (or until treatment is no longer tolerated) and an end of treatment visit at 4 weeks (\pm 7 days) after last treatment.

The End of Study (EOS) defined as either the date of the last visit of the last patient to complete the study, or the date of receipt of the last data point from the last patient that is required for primary, secondary, and/or exploratory analysis, as pre-specified in the protocol.

End of Treatment (EOT) for a patient is defined as the date of the last dose of ABI-009 or nivolumab.

End of Treatment Visit for a patient is when safety assessments and procedures are performed after the last treatment, which must occur at least 4 weeks (\pm 7 days) after the last dose of ABI-009 or nivolumab.

Follow-up period is the on-study time period after the EOT Visit. All patients that discontinue study drug and have not withdrawn full consent to participate in the study will continue in the follow-up phase for survival and initiation anticancer therapy. Follow up will continue approximately every 12 weeks (+/- 3 weeks), until death, withdrawal of consent, or the study closes, whichever is the earliest. This evaluation may be made by record review and/or telephone contact.

